6. STATISTICAL DESIGN

Measures:

Measures will be collected at baseline, weekly thereafter, with primary endpoint of complete healing at Visit 14/Week 14, and final secondary endpoint measurement at Visit 17/Week 31. The ulcer will be assessed weekly and will be treated as described above. A designated inter-observer (blinded to the treatment of the subjects) will regularly review images and physical exam findings to determine primary and secondary endpoints. The following measurements will be taken: size (surface area calculation), photos (digital includes ruler) and complete foot ulcer assessment (description of ulcer/characteristics), before and after debridement. Subjects where ulceration healed earlier than Visit 14/Week 14 will have follow-up assessment one week after healing, a 2nd assessment a week after, then 4 monthly visits at Weeks 19, 23, 27 & 31. If the ulceration healed after 12 weeks, then the subjects will be similarly assessed. The subject with healed ulcer will also return for follow-up visits Weeks 19, 23, 27 & 31 (visits 16, 17, 18 and 19).

During the study, if ulceration appears to be infected as determined by clinical presentation characterized by the presence of two or more signs of inflammation, the clinician will follow the protocol of obtaining wound culture for microbiology, radiographs, blood work (CBC, chemistry panel, sedimentation rate, and C-reactive protein), and treatment immediately with appropriate antibiotics. Subjects with infected ulcers will be withdrawn from study and investigators will be notified. In addition, adverse events will be well documented and treated per protocol, and subjects will be withdrawn from study.

Clinical Outcomes:

- The percentage of subjects that have complete closure of ulceration by Visit 14/Week 14 and Visit 17/Week 31. Complete healing will be defined as full re-epithelialization with no drainage, or callus formation and remains closed after 1 week of wound closure.

- Rate of wound healing to achieve complete closure. Weekly measurements of surface area will be recorded using Silhouette Mobile™ ulcer tracing and surface area calculation.
- A diabetic foot ulcer assessment form will be filled out at weekly follow-up visits, that describes characteristics of ulceration including peri-ulcer erythema, wound margins, fibrin, granular tissue, peri-ulcer pruritus, edema and location, pain, amount of drainage and type, amount of epithelialization, pain level, depth, and bioburden.
- Number of incident subjects with infection, osteomyelitis and acute Charcot during the study, will be withdrawn from the study.
- Number of incidences of adverse effects will be reported from all sites and will be withdrawn from the study.
- VR-36 Health Survey, and the Lower Extremity Functional Scale Outcome Questionnaire (self-administered questionnaires) will be used to measure quality of life and provided at beginning of the study and at the study endpoint.
- Rate of transepidermal water loss will be measured weekly subsequent to wound closure and compared in the two groups.

Sample Size Estimation:

From previous studies, we expect that about 20% of the study subjects will heal in the control arm of our study by the 12th week of care. We estimate that the experimental treatment will improve this outcome with 63% of the study subjects healing by the 12th week of care (a healing rate close to that reported in the most recent case series of topical use of timolol on chronic wounds).

We will perform simple allocation of the subjects using an electronic randomization for treatment assignment-since our target enrollment population is fairly homogenous.

The sample size calculation will require the enrollment of 48 subjects (24 subjects in each arm) to provide a power of 80% to detect a difference of 43% (= 63% - 20%) in the rate of ulcer healing between the two arms by using two-sided Fisher's exact test at a significance level of 5%. It is estimated that the overall attrition will be 35%. Specifically, 10% of the subjects who are enrolled will be exited from the study prior to randomization, 10% will not meet the primary endpoint analysis inclusion requirement and 15% will not complete the study due to other factors such as treatment failure, loss to follow-up, adverse events, clinical/safety issues, and/or non-compliance. We will track the various reasons for study exit. Therefore, 138 subjects (69 subjects in each arm) will be recruited into the study after taking into account the overall attrition of 35%.

The consulting statistician will review implementation and compare major baseline demographic and prognostic characteristics to ascertain that randomization was successful. The power analysis was formulated using the STPLAN Version 4.5 (2010) with the input of the study consultant biostatistician.

Analyses:

The primary outcome is complete ulcer closure by Week 14 (end of the Active Phase) of the study and the rate of ulcer healing by the 12th week of care between the two arms.

[figure not shown]
Hypothesis to be tested: The null hypothesis is that there is no difference in the proportion of subjects with complete wound closure of DFU between the timolol treatment group and the control group. Complete wound closure is defined as 100% closure, or skin re-epithelialization without any drainage present or dressing requirements. Two-sided Fisher's exact test will be used to compare the proportion of complete ulcer closure by Week 12 (end of the Active Phase) of the study and the rate of ulcer healing by the 12th week of care between the two arms. The Kaplan-Meier method will be used to estimate the survival function of time to achieve complete ulcer closure (if less than 12 weeks) for each arm, and a two-sided log-rank test will be used to compare the survival curves between the two arms.

The area of the target ulcer will be summarized by treatment group and visit. Both actual value and change from the previous visits ulcer area will be presented. A second summary of target ulcer area will also be given which will present change from baseline. The weekly change and the percentage weekly change in the target ulcer area from visit to visit will be summarized by treatment group and visit. The two-sided t-test or Wilcoxon rank-sum test as appropriate will be used to compare relative ulcer area from baseline to Week 12 between the two arms.

Chi-square test or Fisher's exact test as appropriate will be used to compare wound healing rates in relationship to wound size, as well as wound healing rates between the treatment groups at the 4-week follow-up and at the 12-week follow-up period and recidivism rate.

Additional secondary analyses to evaluate the association of specific wound characteristics (such as wound size, wound location) and subject characteristics (body mass index, chronicity of the wound, history of DVT, length of diabetes, HbA1c, and ABI/toe pressure will be conducted using logistic regression. Further logistic regression will be used to investigate the relationship between the occurrence of each type of adverse event and treatment in order to adjust for each of the potential confounding factors previously listed. A two-way ANOVA with a post hoc test will be used to determine the relationship between timolol serum levels and wound healing. For demographic and clinical characteristic data at baseline, continuous variables will be summarized (when appropriate) by using mean, median, standard deviation, co-efficient of variation, minimum value and maximum value. Categorical variables will be summarized with frequency tables. Baseline comparability between the two treatment groups will be assessed by using the independent two-sample t-test or Wilcoxon rank-sum test and the Chi-square test or Fisher's exact test. Finally, we will use ANCOVA to analyze the quality of life (QOL) using the VR-36 Health Survey and the Lower Extremity Functional Scale Outcome Questionnaire, and the Charlson Comorbidity Index.

Timeline and Milestones:

7. APPENDIX 1 – Wound Scoring System

Ulcer Characteristic Form

Size: Dimensions _____ x _____ x _____ cm

Number of leg ulcers: Right Leg _____ Left Leg _____

If multiple ulcers, write distance from the study ulcer to other ulcers: _____ cm

Where is the study ulcer located? Right Leg Left Leg

Describe the study ulcer location: foot ankle low calf high calf other:

Describe the study ulcer position: dorsal ventral medial anterior lateral
 posterior

How old is the current target diabetic foot ulcer (in weeks): _____ weeks

Event that precipitated target ulcer: Ill-fitting shoes Poor foot care Acute accidental event (trauma) Not determined Other, please specify: _____

Has the study ulcer ever healed and recurred? Yes No

Has the subject ever suffered a DVT in the study limb? Yes No

Does the Study Limb/Leg Ulcer present with any of the following? (Check all that apply)

Hyperpigmentation Varicosities Dermatitis Swelling/Edema
 Lipodermatosclerosis Other: _____

	Parameter	Assessment	Score	Total
1	Erythema	Absent	0	
		Mild	1	
		Moderate	2	
		Severe	3	
2	Induration	Absent	0	
		Mild	1	
		Moderate	2	
		Severe	3	
3	Tenderness	Absent	0	
		Mild	1	
		Moderate	2	
		Severe	3	
4	Pain	Absent	0	
		Mild	1	

		Moderate	2	
		Severe	3	
5	Local warmth	Absent	0	
		Mild	1	
		Moderate	2	
		Severe	3	
6	Size (cm ²)	<1	0	
		1–2	1	
		> 2–5	3	
		> 5–10	6	
		> 10–30	8	
		> 30	10	
7	Depth (mm)	<5	0	
		5–9	3	
		10–20	7	
		> 20	10	
8	Undermining (mm)	< 2	3	
		2–5	5	
		> 5	8	
TOTAL SCORE				

Wound Assessment Tool Interpretation

1. **Erythema**, congestive or exudative redness surrounding the wound caused by engorgement of the capillaries in the lower layers of the skin. Grade: none: absent; mild: pink, barely perceptible; moderate: pale red with defined edges; severe/extreme: red to dark red.
2. **Induration**, inflammatory hardening or thickening of tissues. Grade: none: absent; mild: localized to the site of infection; moderate: limited extension from the site of infection; severe: extending from the site of infection to involve a substantial portion of the affected lower extremity.
3. **Tenderness** (sign), palpation of the site elicits a report by the patient of tenderness; measured on a 0 (no tenderness) to 10 (the worst imaginable tenderness) scale. Grade: none: absent; mild: score of ≤ 5 ; moderate: score of 6–8; severe: score of ≥ 9 .
4. **Pain** (symptom), subjective reporting of discomfort or the perception of pain at the site of the wound as reported by the patient; measured on a 0 (no pain) to 10 (the worst imaginable pain) scale. Grade: Grade: none: absent; mild: score of ≤ 5 ; moderate: score of 6–8; severe: score of ≥ 9 .
5. **Local warmth** (sign), Increase in skin temperature relative to the uninfected contralateral foot. Grade: none: temperature of the two sides the same; mild: temperature slightly, but perceptibly warmer; moderate: temperature clearly warmer; severe: marked difference in temperature.
6. **Size (cm²)** - the ulcer area.

7. **Depth** (mm) - measured in the deepest apparent part of the wound using a sterile cotton-tipped wooden swab held 90° to the wound and marked with a pen held parallel to the surface of the intact skin.
8. **Undermining** (mm), measurement of any tunneling, subepithelial tissue loss, or shearing, as measured using a sterile cotton-tipped wooden swab.

Lipsky *et al.* The value of a wound score for diabetic foot infections in predicting treatment outcome: a prospective analysis from the SIDESTEP trial. *Wound Repair Regen.* 2009 Sep-Oct;17(5):671-7. Epub 2009 Aug 11.

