24. Prisoners, institutionalized individuals or vulnerable population
(The real-world group will not have any exclusion criteria related to timolol (criteria 18-22)

(*)Note: The exclusion criteria were modified compared to the original submission based on the recommendation from the DMC, which suggested that these criteria would significantly impair the enrollment. Those were also revised upon evaluation by the consultant Cardiologist, [name].

TREATMENT: Total duration of study per subject: Up to 31 weeks (Includes to 2 weeks of screening and up to 16 weeks until the end of the follow-up period). 12 weeks for the real-world group.

DURATION OF ADMINISTRATION: Daily application for 12 weeks (starting at Visit 3/Week 3).

STUDY DESIGN: This is a prospective, randomized, double blinded, controlled, and parallel-group study with 2 arms: β AR antagonist (SOC plus topically applied Timoptic-XE®) and control (standard of care (SOC) plus non-biologically active gel (hydrogel, Kendall®, placebo medication)).

EFFICACY ENDPOINTS:**PRIMARY EFFICACY OUTCOME**

1. Complete closure of ulcer by Visit 14/Week 14

SECONDARY EFFICACY OUTCOME

1. Complete closure of ulcer by Week 31
2. Percent difference change in size from the randomization visit to the endpoint visit (post 12 weeks)
3. Time to wound closure
4. Rate of ulcer healing
5. Change in transepidermal water loss of re-epithelialized wound after wound closure

SAFETY ENDPOINT:**PRIMARY SAFETY OUTCOME**

1. Timolol serum levels during the treatment phase

SECONDARY SAFETY OUTCOME

1. Mean changes from baseline in systolic and diastolic blood pressure in mmHg
2. Mean changes from baseline in heart rate in beats per minute
3. Adverse events associated with the use of timolol.

QUALITY OF LIFE ASSESSMENT: We will use ANCOVA to analyze the quality of life from the VR-36 Health Survey and the Lower Extremity Functional Scale Outcome Questionnaire.

DATA ANALYSIS:

The primary outcome is complete ulcer closure by Week 12 (end of the Active Phase) of the study and the rate of ulcer healing by the 12th week of care between the two arms.

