For demographic and clinical characteristic data at baseline, continuous variables will be summarized (when appropriate) by using mean, median, standard deviation, co-efficient of variation, minimum value and maximum value. Categorical variables will be summarized with frequency tables. Baseline comparability between the two treatment groups will be assessed by using the independent two-sample t-test or Wilcoxon rank-sum test and the Chi-square test or Fisher's exact test.

Following wound closure, comparison of changes in the epidermal barrier function of healed ulcers treated with timolol vs those treated with saline control will be non-invasively measured quantitating the transepidermal water loss (TEWL). Categorical variables will be summarized with frequency tables. Baseline comparability between the two treatment groups will be assessed by using the independent two-sample t-test or Wilcoxon rank-sum test and the Chi-square test or Fisher's exact test.

TABLE OF CONTENTS

- 1 BACKGROUND AND RATIONALE
- 2 OBJECTIVES
- 3 STUDY POPULATION
- 4 STUDY PROCEDURES
 - 4.1 DESIGN AND METHODOLOGY
 - 4.2 DESCRIPTION OF STUDY GROUPS
 - 4.3 STUDY FLOW CHART
 - 4.3.1 SCREENING/BASELINE PERIOD (VISIT 1 to 2/WEEKS 1 to 2)
 - 4.3.2 RANDOMIZATION (VISIT 3/WEEK 3)
 - 4.3.3 TREATMENT PHASE (VISIT 4/WEEK 4)
 - TREATMENT PHASE (VISIT 5/WEEK 5)
 - TREATMENT PHASE (VISIT 6/WEEK 6)
 - TREATMENT PHASE (VISIT 7/WEEK 7)
 - TREATMENT PHASE (VISIT 8/WEEK 8)
 - TREATMENT PHASE (VISIT 9/WEEK 9)
 - TREATMENT PHASE (VISIT 10/WEEK 10)
 - TREATMENT PHASE (VISIT 11/WEEK 11)
 - TREATMENT PHASE (VISIT 12/WEEK 12)
 - TREATMENT PHASE (VISIT 13/WEEK 13)
 - TREATMENT PHASE (VISIT 14/WEEK 14)
 - 4.3.4 STUDY ENDPOINT (VISIT 14/WEEK 14)
 - 4.3.5 2ND CONFIRMATORY VISIT (VISIT 15/WEEK 15)
 - 4.3.6 FOLLOW-UP PHASE (VISIT 16/WEEK 19)
 - FOLLOW-UP PHASE (VISIT 17/WEEK 23)
 - FOLLOW-UP PHASE (VISIT 18/WEEK 27)
 - FOLLOW-UP PHASE (VISIT 19/WEEK 31)
 - 4.3.7. REAL-WORLD GROUP PHASES
 - SCREENING/BASELINE PERIOD (VISIT 1/WEEK1)
 - FOLLOW-UP PHASE (VISIT 2/WEEK 6)
 - STUDY ENDPOINT (VISIT 3/WEEK12)
 - 5 ADVERSE EVENTS
 - 6 STATISTICAL DESIGN
 - 7 APPENDIX 1 – Wound scoring system
 - 8 APPENDIX 2 – Hemostasis procedure
 - 9 APPENDIX 3 – Infection exclusion procedure
 - 10 APPENDIX 4 – Home Care Instructions

- 11 APPENDIX 5 – Veterans Rand-36 (VR-36) Health Survey**
- 12 APPENDIX 6 – Lower Extremity Functional Scale**
- 13 APPENDIX 7 – Charlson Comorbidity Index**

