1.1. STUDY FLOW CHART

Study Plan Schematic

Procedure	Screening Phase Visits 1-2 (Week 1-2)		Active Phase Visits 3-14 (Week 3-14) Including a 1st confirmatory visit if healed before 12 weeks of treatment		2nd Confirmatory Visit Prior to Follow-up Phase Visit 15 (Week 15)	Follow-up Phase Visits 16, 17, 18 & 19 (Week 19, 23, 27 & 31)			
	Visit 1 (Week 1)	Visit 2 (Week 2)	Visit 3 (Week 3) Randomization	Visits 4-14 (Week 4-14) Study Endpoint at Week 14*	Visit 15 (Week 15)	Visit 16 (Week 19)	Visit 17 (Week 23)	Visit 18 (Week 27)	Visit 19 (Week 31)
Inclusion/Exclusion Criteria	X	X	X						
Informed Consent/HIPAA document	X								

VR-36 Health Survey Questionnaire	X			X*					
Lower Extremity Functional Scale Outcome Questionnaire	X	X		X					X
Charlson-Comorbidity Index	X								
Physical Exam	X			X*					
EKG	X			X*					
Vital Signs	X	X	X	X	X	X	X	X	X
Ankle-Brachial Index/Duplex Scan	X	X							
Debrided Tissue for genetic analysis (Weeks,1-9)	X	X	X	X					
Bacterial, Fungal Infection and Malignancy Evaluation	X								
Laboratory evaluation (hematology, renal, and liver function)	X								
Vapometer Readings@ (@If healed, readings recorded from point of closure + 4 months)				X@	X	X	X	X	X
Blood Sample for Timolol assay/Inflammatory markers(weeks 4,8,12)	X			X†					
Ulcer Assessment	X	X	X	X	X	X	X	X	X
Debridement († if needed)	X	X	X	X	X†	X†	X†	X†	X†
Ulcer Photography and Area Measurement	X	X	X	X	X	X	X	X	X
Offloading device	X	X	X	X	X	X	X	X	X
Randomization			X						
SOC + Timoptic-XE@ or SOC + non biologically active gel (hydrogel as placebo medication)			X	X					

SOC			X	X	X	X	X	X	X
Concomitant Medications and Adverse Events	X	X	X	X	X	X	X	X	X

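### The Week 31 closure endpoint carries the wrong visit number, and its one-week confirmation rule cannot be met by an ulcer first seen closed at Week 31

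*Combined protocol and SAP*

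**What the plan says.** The Protocol Summary lists as its first secondary efficacy outcome "Complete closure of ulcer by Week 31", defined by week with no visit number. Section 6 adds a visit number twice. Under Measures it gives the "final secondary endpoint measurement at Visit 17/Week 31". Under Clinical Outcomes it gives the percentage with "complete closure of ulceration by Visit 14/Week 14 and Visit 17/Week 31".

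The contents list has "FOLLOW-UP PHASE (VISIT 17/WEEK 23" and "FOLLOW-UP PHASE (VISIT 19/WEEK 31". The flow chart heads the follow-up columns "Visits 16, 17, 18 & 19 (Week 19, 23, 27 & 31". Section 4.3.3 and a later sentence under Measures in Section 6 use the same map.

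On confirmation, the Clinical Outcomes bullet that names the Week 31 endpoint requires that the ulcer "remains closed after 1 week of wound closure". Measures gives ulcers healed before Week 14 an assessment one week after healing, another a week later, and then the fixed visits at Weeks 19, 23, 27 and 31. It continues: "If the ulceration healed after 12 weeks, then the subjects will be similarly assessed". Section 4.3.3 says that subjects whose ulcer is still open after 12 weeks of application are seen monthly. The Protocol Summary limits participation to 31 weeks. The closure definitions in the Protocol Summary (objectives and data analysis), Section 2 and the Analyses part of Section 6 contain no one-week element.

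**The concern.** Two things in the statistical section do not fit the schedule. The visit number attached to the first-listed secondary efficacy endpoint belongs to a different week, so a data set built by visit number would stop at Week 23. Separately, the healing definition needs an observation one week after closure, while scheduled visits after Week 15 are four weeks apart and end at Week 31. Whether a late closure counts would then depend on which definition the analyst picks and on whether an unlisted visit took place. Both should be settled before the data are seen.

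**Working it through.** **Visit map.** From the contents list and flow chart, Visits 1 to 15 fall at Weeks 1 to 15, and Visits 16, 17, 18 and 19 at Weeks 19, 23, 27 and 31. Visit 17 is therefore Week 23, and Week 31 is Visit 19. The Section 6 label does not reproduce: 31 − 23 = 8 weeks, and the last two of the four follow-up visits (18 and 19) would be left out.

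**One-week check against the schedule.** For each week at which closure is first seen:

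| First seen closed | Scheduled visit one week later? | Next scheduled visit |
|---|---|---|
| Week 12 | yes | Week 13 |
| Week 13 | yes | Week 14 |
| Week 14 | yes | Week 15 |
| Week 15 | no | Week 19 (4 weeks) |
| Week 19 | no | Week 23 (4 weeks) |
| Week 23 | no | Week 27 (4 weeks) |
| Week 27 | no | Week 31 (4 weeks) |
| Week 31 | no | none |

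**What the text adds.** "If the ulceration healed after 12 weeks, then the subjects will be similarly assessed" extends the checks at one and two weeks to late healers. These would fall at Weeks 16 and 17 for closure at Week 15, 20 and 21 for Week 19, 24 and 25 for Week 23, and 28 and 29 for Week 27. All lie within 31 weeks, but neither the flow chart nor Section 4.3.6 lists them, and they sit awkwardly with monthly follow-up in Section 4.3.3. For Week 31 the checks would fall at Weeks 32 and 33, outside the maximum, so no reading of the text supplies a confirmation.

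**Which definition applies.** Under the Clinical Outcomes definition, a first closure at Week 31 cannot count, and the last scheduled visit at which a first closure can qualify is Week 27. Under the Analyses definition, which has no durability requirement, the same ulcer counts. The two definitions therefore give different Week 31 proportions whenever an ulcer is first seen closed at Visit 19. With 24 subjects per arm, each such ulcer moves the proportion by 1/24 = 4.2 percentage points.

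**The case against.** The strongest reply is that the label is a typing error with little consequence. Both instances print Week 31, the Protocol Summary fixes the endpoint by week alone, and Section 6 itself gives the correct map a few lines later. That largely stands: misextraction is unlikely, though the endpoint definition is still wrong as written.

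The second reply is that late closures do have a confirmation, through the sentence that extends the early-healer assessments. This stands for Weeks 15, 19, 23 and 27, where the defect is a promised check missing from the schedule. It does not help at Week 31. A reader might also infer that the extended assessments overrun the study, with four new monthly visits after a Week 23 closure ending at about Week 41. The text does not support this, because it fixes the monthly visits at Weeks 19, 23, 27 and 31 and does not restart them at closure.

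The third reply is that few subjects are involved. The documents give no late-closure rate, so this can only be illustrated. Assume a constant weekly hazard in both arms taken from 20% healed at 12 weeks (Section 6) and 31% at 20 weeks (Section 1): ln(0.80/0.69)/8 = 0.0185. Taking Week 14 as 12 weeks of care, the fraction of ulcers open at that point that close between Weeks 27 and 31 is exp(−13 × 0.0185) × (1 − exp(−4 × 0.0185)) = 0.056. That gives 24 × 0.80 × 0.056 = 1.1 control and 24 × 0.37 × 0.056 = 0.5 timolol subjects. Halving or doubling the hazard gives 0.6 to 1.6 and 0.3 to 0.8. On these assumptions the number is small.

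A reader might infer from the larger share of open control ulcers that the gap favours timolol. That rests on the equal-hazard assumption: the direction would reverse if late closure among open timolol ulcers were more than about 0.80/0.37 = 2.2 times as frequent. Nothing in the documents settles this. Nor do they establish that confirmation would differ between sites, since the Protocol Summary names one central study location, although Section 4.3.3 mentions appointments at each VA facility.

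**Conclusion.** The point holds in a limited form. The visit label in Section 6 is wrong in both places, by 8 weeks. The one-week rule excludes any ulcer first seen closed at Week 31, so read literally the endpoint is closure first seen by Week 27. For first closures at Weeks 15 to 27 the text and the flow chart disagree about whether a one-week check takes place. Which closure definition governs is itself unsettled.

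This affects a secondary endpoint only. No size or direction of bias is claimed. The conclusion on Week 31 assumes that the 31-week maximum is binding and that the Clinical Outcomes definition applies to this endpoint, as its placement in the same bullet suggests.

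**What to change.** 1. Change the label to Visit 19/Week 31 in both places in Section 6.
2. State which closure definition governs the Week 31 endpoint, and use it throughout.
3. Reconcile the flow chart, Sections 4.3.3 and 4.3.6, and Section 6 on the one-week check for ulcers first seen closed at or after Visit 15.
4. Pre-specify, identically in both arms, that first closures at Visit 19 are reported as a separate unconfirmed line, and show the Week 31 proportion with and without them.

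Accepting the next monthly visit as confirmation would be simpler but is not advised: it would ask for four weeks of durability from late closures against one week from early ones. Dropping the later checks would be more than a wording change, since Section 6 also plans weekly water-loss readings after closure.

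The cost is wording, one extra line of analysis, and an unconfirmed flag on Week 31 closures. If item 3 is settled by listing the promised checks, the flow chart gains those visits.

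### The plan withdraws randomised subjects for reasons tied to non-closure and books treatment failure as attrition, but gives no analysis set, no rule for counting exits and no censoring rule

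*Combined protocol and SAP*

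**What the plan says.** **Withdrawal.** Section 6 (Measures) states "Subjects with infected ulcers will be withdrawn from study and investigators will be notified" and, for other events, that "adverse events will be well documented and treated per protocol, and subjects will be withdrawn from study". The Clinical Outcomes list adds "Number of incident subjects with infection, osteomyelitis and acute Charcot during the study, will be withdrawn from the study". Section 3 (Withdrawal) lets the investigator discontinue a subject for non-response, an adverse event needing other therapy, or non-compliance. Section 4.3.3 ends participation at a serum timolol level of 0.7 ng/ml or higher.

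**Attrition.** Section 6 (Sample Size Estimation) splits 35% overall attrition into three parts. The first is a 10% loss before anyone is randomised. The second reads "10% will not meet the primary endpoint analysis inclusion requirement", and that requirement appears nowhere else in the documents. The third reads "15% will not complete the study due to other factors such as treatment failure", and its list of reasons goes on to cover lost contact, safety and poor compliance. On exits the text adds only "We will track the various reasons for study exit".

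**Analysis.** The Protocol Summary (Data Analysis) and Section 6 (Analyses) compare the proportion of subjects closed by two-sided Fisher's exact test, and time to closure by Kaplan-Meier and log-rank. Neither names an analysis set, a rule for withdrawn subjects, a missing-data method or a censoring rule.

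**Follow-up.** Section 3 (Withdrawal) follows treated subjects to the end of the study, and plans added recruitment if loss to follow-up exceeds 10%. Section 4.3.3 follows ulcers still open after 12 weeks of application monthly until study completion.

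**The concern.** Non-response is failure on the primary endpoint, and infection and osteomyelitis are plausible routes to it. If such subjects leave the denominator, the test runs on a group selected partly by the outcome. Closure rates then rise in each arm, and the treatment difference is biased if the share of non-closers removed differs by arm.

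With no rule in the plan, the denominator can be settled after outcomes are known. Blinding does not prevent this, because dropping someone for not healing requires no knowledge of the arm. The same gap affects the log-rank test: censoring a subject at withdrawal for infection or non-response treats that exit as unrelated to the chance of closing.

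**Working it through.** **1. The plan's own figure.** Inputs from Section 6: 63% vs 20%, two-sided Fisher's exact test at 5%, 80% power, 24 per arm. Exact enumeration of the two binomials gives power of 79.5% at 23 per arm and 82.5% at 24. The 24 per arm reproduces.

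**2. Size of the exits.** Of 100 enrolled, 10 leave before randomisation, so 90 are randomised. The 15% who do not complete are 15/90 = 16.7% of those randomised. If the 10% failing the undefined requirement also leave after randomisation, the figure is 25/90 = 27.8%. The 15% refers to completing a study that runs to Week 31, so some of these exits may come after Week 14 with the primary outcome already recorded. The range is therefore an upper range for loss before the primary endpoint.

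**3. Equal removal of non-closers.** If a share r of non-closers is dropped, the apparent rate is p / (p + (1 − p)(1 − r)).
- r = 0.2: 0.63/0.926 = 68.0% vs 0.20/0.84 = 23.8%, a difference of 44.2 points.
- r = 0.6: 0.63/0.778 = 81.0% vs 0.20/0.52 = 38.5%, a difference of 42.5 points.

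Both rates rise, but the difference stays close to the planned 43 points.

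**4. Unequal removal, no drug effect.** With 24 randomised per arm, closers are Bin(24, p) and retained non-closers are Bin(24 − closers, 1 − r). Rejection means Fisher p ≤ 0.05. The splits by arm and the true closure rates are assumptions.

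| Non-closers removed (timolol vs control) | 40% true closure | 20% true closure |
|---|---|---|
| none | 2.7% | 2.6% |
| 20% vs 10% | 3.4% | 3.4% |
| 30% vs 10% | 4.5% | 4.1% |
| 40% vs 10% | 6.7% | 5.8% |

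Reversing the 40% vs 10% split at 40% closure gives the same 6.7%, nearly all of it favouring control.

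**5. A single trial.** Suppose 12/24 vs 5/24 close: p = 0.069. Drop six non-closers from each arm (6/24 = 25%, inside the range in step 2) and the table is 12/18 vs 5/18: p = 0.044. The number dropped is equal, but it is 6/12 = 50% of the timolol non-closers and 6/19 = 32% of the control non-closers.

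**6. Power if everyone is counted, 24 randomised per arm.**
- 63% and 20% already apply to all randomised: 82.5%.
- They are completer rates, 16.7% exit before the endpoint, and exits count as not closed: 0.63 × 75/90 = 52.5% vs 0.20 × 75/90 = 16.7%, power 67.5%.
- The same with 27.8% exits: 0.63 × 65/90 = 45.5% vs 0.20 × 65/90 = 14.4%, power 56.9%.

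**The case against.** The strongest reply is that the plan has the pieces of a sound analysis. Withdrawal triggers are listed, treated subjects are followed to the end of the study, open ulcers are followed monthly, the trial is double-blind, and a blinded reviewer determines the endpoints. The sample-size text applies 63% and 20% to the study subjects, not to completers. The calculations also show limited harm: at 24 per arm, rejection under no effect passes 5% only at the most unequal split tried, and every split is assumed.

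Most of this stands. A reader might infer that the plan has no withdrawal criteria, but it has several; the missing rule is how exits are counted. A reader might infer that exclusion of withdrawn subjects is prescribed, but no section says so. A reader might infer a bias towards timolol. The documents do not support a direction: the one trigger that in practice can arise only on timolol is the serum level, and Section 4.3.3 does not expect levels above those seen with ocular use. A reader might also take 16.7% as the least that will be lost before the primary endpoint, which ignores exits after Week 14.

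The gap remains. Follow-up makes an all-randomised analysis feasible without specifying one. Blinding leaves the denominator open. Booking treatment failure and an analysis inclusion requirement as attrition makes an evaluable-subject test the natural reading of the sample-size text.

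**Conclusion.** The point holds as a failure to pre-specify. The plan withdraws subjects for outcome-related reasons, implies that some are left out of the primary test, and fixes neither the denominator nor the censoring. Exits may reach 16.7% to 27.8% of those randomised, as an upper range before the endpoint. Leaving out non-closers raises closure in both arms. It distorts the difference only if the share removed differs by arm, and then in either direction. Inflated type I error at 24 per arm is a possibility under strong assumed imbalance, not a demonstrated result. The firmer reason to act is that, with 48 subjects, a choice of denominator made after the data are seen can move a result across 5%.

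**What to change.** In Section 6 and the matching Protocol Summary text:

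- State that the primary Fisher test includes every randomised subject in the assigned arm. A subject counts as closed if closure meets the protocol's full definition by the endpoint visit and is confirmed one week later (Section 6 already requires that the ulcer "remains closed after 1 week of wound closure"), even if the subject has been withdrawn by then. Every other randomised subject counts as not closed. This needs one closure definition and one endpoint visit, since the text uses both Week 12 and Week 14.
- Delete the primary-endpoint inclusion requirement, or define it and use it only for a secondary completer analysis.
- State that subjects recruited because of loss to follow-up are added and do not replace anyone randomised.
- For Kaplan-Meier and log-rank, keep withdrawals without confirmed closure at risk to the endpoint visit, with censoring at exit as a sensitivity analysis. Other rules could be defended, but one must be fixed in advance.
- Reconcile Section 3 (followed to the end of the study) with Section 6 (withdrawn from it) so that the endpoint ulcer assessment is still collected where the subject agrees. No clinical withdrawal rule need change for this.
- State whether 63% and 20% refer to all randomised subjects or to completers, and restate the power.

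**Cost.** The work is mainly wording, plus endpoint assessments after withdrawal, which will not be possible for every subject. Observed closure rates become more conservative. If the rates apply to all study subjects, as the wording suggests, 24 per arm keeps 82.5% power. If they are completer rates and all exits precede the endpoint, 80% power needs 31 per arm (16.7% exits) or 38 per arm (27.8% exits).
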